manage the most emotionally challenging and destructive symptoms for families and caregivers. Our group has identified oxytocin as a candidate treatment for the social apathy and indifference patients with FTD develop towards others. Growing evidence indicates that the neuropeptide oxytocin is an important mediator of social behaviour across species. Our early studies of intranasal oxytocin in patients with FTD have demonstrated improvements in neuropsychiatric behaviours, specifically in social apathy and empathy. We propose a novel proof-of-concept phase 2 adaptive design trial, repurposing the hormone and neuropeptide oxytocin as a potential symptomatic treatment for apathy/indifference and related empathy deficits in patients with FTD. We will examine different dose schedules of oxytocin (intermittent and daily) given concerns in animal models of potential habituation of effects when oxytocin is chronically administered. If effective, oxytocin would be the first symptomatic treatment for patients with FTD specifically targeting the core deficits in social apathy so devastating in this disorder.

Objectives

Research Question:

Is intranasal oxytocin an effective symptomatic treatment for improving social apathy/indifference deficits and related behaviour in patients with FTD?

Primary Efficacy Objective

Change in Neuropsychiatric Inventory (NPI) apathy/indifference domain score

Secondary objectives:

- Change in emotional facial expression recognition performance
- Change in the Interpersonal Reactivity Index (IRI) empathic concern scale and IRI total score
- Change in the Revised Self-Monitoring Scale (RSMS) score
- Change in modified Clinicians Global Impression of Change (m-CGIC) scores (directed to apathy)
- Change in Caregiver Distress Scores on NPI apathy/indifference scale and Caregiver Distress Scores on Total NPI
- Change in total NPI scores
- Difference in CSF oxytocin levels (oxytocin vs. placebo treatment periods) (optional substudy)

Safety Measures:

- Adverse symptoms
- Changes in serum sodium levels, heart rate and blood pressure
- Change in QTcF as measured by ECG
- Compliance with treatment (based on daily logs and measurement of residual volumes)

Exploratory Measures:

- Change in social behaviours based on videotaped segments of naturalistic behaviour
- Examination of impact of oxytocin receptor (OXTR) polymorphisms on behavioural outcome measures.

Section 3: Study Methods

3.1 Trial Design

This is a multi-centre double blind, placebo-controlled randomized cross-over study comparing 6 weeks of oxytocin treatment to 6 weeks of placebo with a 6-week washout between periods. A phase II adaptive design will be used to efficiently identify promising dose schedules and obtain meaningful efficacy data. In Stage 1 of the study, we will evaluate three dosing schedules compared to placebo: daily dosing, alternate day dosing, and every 3rd day dosing. At the end of Stage 1, Bayesian analysis will be conducted to identify the most promising dose schedule, termed the “target dose”. In Stage 2, additional patients will be enrolled at the target dose schedule. In both stages the primary outcome measure is change on the NPI apathy/indifference domain score from baseline. At the end of Stage 2, data from patients receiving the target dose (from Stage 1 and Stage 2) are combined in the efficacy analysis. An optional CSF sub-study

measuring oxytocin levels during oxytocin vs. Placebo periods will confirm CSF oxytocin level rises in FTD and determine whether changes in CSF oxytocin levels correlate with behavioural measures.

The study is double blinded, participants and all study staff aside from central drug coordinator and unblinded DSMB members will be blinded to dose and arm. In Stage 2 of the study, the study staff and participants will be blinded to dose (at the suggestion of the DSMB and TSC) and arm. Randomization occurs after screening data is accessed and the participant deemed eligible but prior to baseline appointment. In some instances, this meant that participants were randomized into the trial without ever attending a baseline appointment.

3.2 Randomization

Randomization for stage 1 and 2 will be stratified across the treatment groups listed above according to sex and disease severity (CDR score of 0-1 mild vs. CDR score of 2 moderate). Given the number of centres required for a trial in FTD, the study will not be powered to stratify randomization according to centre. Participants will be randomized using variable block sizes concealed from participating sites. Central randomization will occur with web-based Guide 98 and 21CFR11 compliant technology. Central drug coordinator is responsible for randomization and identification of blinded kit assignment. Site coordinators will be provided with kit receipts to provide to local blinded pharmacy for dispensing of appropriate kit on baseline visit days. Only compounding pharmacy and central drug coordinator have access to kit treatment allocation. Central drug coordinator was sequestered and had no contributions to the study other than ordering and tracking kits, and kit assignment.

3.3 Sample Size

The details on the operating characteristics of the adaptive design, including sample size calculation and justification can be found in section 6.1 of the protocol.

3.4 Statistical Interim analyses and stopping guidance (if applicable)

An interim analysis was conducted to select a dose during Stage 1 of the trial design for Stage 2. Details on the interim analysis can be found in protocol Section 6.0 and 6.1.

A futility analysis was not originally planned as part of the original protocol. Due funding and enrolment challenges an administrative analysis took place in October of 2022. Details of this analysis are available in the “Administrative Analysis of FOXY Trial for Frontotemporal Dementia 04 October 2022” document. This administrative analysis does not impact the sample size nor analytic plan.

3.5 Timing of final analysis

The final end of treatment visit occurred in June 2023. Following this, the data will be cleaned, verified, and locked. Collection of SOI and biosamples back to central coordinating site will commence as each site finalizes their individual participation. Analysis of primary outcome measure will commence once the relevant data set has been locked, and the statistical analysis plan is finalized by blinded statisticians and investigators.

3.6 Timing of outcome assessment

Screening window is 0–28-days followed immediately by Baseline 1 assessments. Initial dose of treatment occurs at baseline appointment but after baseline visit outcome assessments have occurred. Baseline 1 treatment window is 42 days +/- 3 days and then End of Treatment visit 1 assessments occur. The final dose of treatment occurs at the beginning of treatment visit prior to End of Treatment 1 outcome assessments. Then a 42 day +/- 3 days washout. Baseline 2 treatment window is 42 days +/- 3 days and then End of Treatment visit 2 assessments occur. The final dose of treatment occurs at the end of treatment visit 2 prior to outcome assessments.

Section 4: Statistical Principles

The trial has a 2-stage design:

In Stage 1 the trial will compare three dosing schedules of 72 IU intranasal oxytocin (daily, alternate day, or every 3rd day dosing) for patients with FTD compared to placebo. Twenty participants per arm will be randomized to each of the three dose arms and order of the cross-over (order of oxytocin and placebo). All dose schedules will use sprays bid (morning and afternoon, with placebo on non-oxytocin Rx days) to maintain blinding to schedule across all of the cohorts. After 6 weeks, patients will have a 6-week washout period and then cross-over to the other treatment arm (placebo to oxytocin; oxytocin to placebo). After 60 participants have completed their participation, interim Bayesian analysis will determine which of the dosing schedules appears most promising. For Stage 2, the most promising dose schedule, designated the “target dose,” will be carried forward for the remainder of participants n=40 who will complete the exact same procedures as participants in Stage 1. Data from the target dose group from stage 1 and 2 will be combined for the final analysis.

4.1 Confidence Intervals and P-values

Stage 1 and Stage 2 for the target selected treatment arm will be used to test superiority using a nominal 2.5% one-sided test for the primary outcome of change in NPI.

All secondary, safety and exploratory outcomes will be reported as two-sided tests with statistical significance set at a two-sided 0.05 level.

4.2 Adherence and protocol deviations

Adherence to treatment is assessed by participant drug diary. Caregivers completed the diary with doses completed and missed. These notes were confirmed by study coordinators at EOT visits and are used to assess compliance. The compliance notes are cross-referenced with bottle weights to confirm medication dispensed.

For safety ECG data, per-protocol analysis will include ECGs obtained within the 0–25-minute window following IP treatment. Sensitivity analysis will also include those obtained outside the window of 15–25 min post-treatment. Sensitivity analysis of primary and secondary outcomes will exclude patients who had the addition of a new medication targeting behaviour or cognition during either of the treatment periods.

For assessments completed by caregiver, the data must be collected within 30 days of last dose of IP.

For cognitive outcomes completed by patient, data must be collected within 3 days of last dose of IP.

Data for which there are clear validation errors or where administration errors are clear and unreconcilable for neuropsychological testing will also be excluded from PPP. Exclusion for validation errors will only be possible for IRI and RSMS where such validation errors are apparent.

Protocol deviations were identified throughout the administration of the trial by CRO and central data coordinator.

4.3 Analysis populations

Intent-to-Treat Population (ITT) - All participants who were randomized and completed at least one baseline assessment.

Modified Intent-to-Treat Population (MITT) - The modified intent-to-treat population is defined as all participants in the ITT Population, but excluding those that did not complete at least one treatment period. Analysis will compare relative period effects for PBO and OXY periods on change in scores from Baseline to End of Treatment.

Per protocol Population (PPP) - All participants who completed each protocol specified study visit and who were at least 70% compliant in study drug administration for both treatment periods. For assessments completed by caregiver, the data must be collected within 30 days of last dose of IP. For cognitive outcomes completed by patient, data must be collected within 3 days of last dose of IP. Data for which there are clear validation errors or where administration errors are clear and unreconcilable for neuropsychological testing will also be excluded from PPP. Exclusion for validation errors will only be possible for IRI and RSMS where such validation errors are apparent.

A CONSORT diagram, detailing the participants excluded from each subsequent population restriction will be presented for the study.

Section 5 – Trial Population

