5.2 Withdrawal/Follow-up

For participants who withdraw from the study for reasons other than death or participant or study partner consent withdrawn, a visit should be scheduled as soon as possible after the last dose of study drug and identified end of treatment safety evaluations performed. For participants who withdraw consent or when a study partner withdraws consent without available alternate study partner, the investigator should request that the reason be specified, and the participant have any clinically indicated safety assessments performed.

Participants in whom treatment is discontinued or who are lost to follow-up should be encouraged to return for a post-treatment visit as soon after the last dose of study drug possible. Participants withdrawn from the study will not be replaced nor can they be re-enrolled.

If a participant is unable to complete the EOT visit, acquired data will be included in the analysis. For patients withdrawing from the study, if they cannot complete an in-person visit, outcome measures that can be acquired via a telephone interview with the study partner/caregiver will be obtained whenever possible.

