6.2 Analysis Methods

The primary analysis of the change from baseline NPI apathy domain is based on a linear model with covariates for sex and order of treatment in the crossover including data from both Stage 1 and Stage 2 for the target selected treatment arm (ETD) will be used to demonstrate superiority using a nominal 2.5% one-sided test using the PPP. Estimated mean effect of the treatment compared to placebo and 95% confidence intervals will be reported. Analysis will compare relative period effects for PBO and OXY periods via change in scores from Baseline to End of Treatment visit.

Supportive primary analysis will be conducted on the MITT population. Given the crossover design, the ITT analysis excludes those that did not take any study medications in their second treatment period.

Sensitivity analysis combining all dose groups for OXY vs. PBO will be conducted for all primary, secondary, and exploratory outcome measures.

Covariates:

Order of treatment (End of treatment 2: Oxytocin versus End of Treatment 2: Placebo)

Sex (male vs female)

Subgroup analyses:

By sex

By severity

Age (median split : young <67 years; older 67+ years)

Oxytocin Genetic polymorphism (GG vs AG vs AA)

FTD subtype (bvFTD vs PNFA vs SD)

ALL other outcomes as listed above, will be analysed using the same methods as for the primary outcome using 5% 2-sided test. Subject is modeled as a random effect, the others are all fixed effects.

To explore whether hormonal levels or imaging atrophy patterns predict behavioural response to OXY, we will conduct a linear regression with NPI apathy domain change scores for OXY-PBO as the dependent measure and predictors of regional MRI atrophy ratings (scores from the Harper et al. visual rating scale for each of the following regions: orbitofrontal, rostral anterior cingulate, fronto-insula, medial temporal, and posterior), baseline serum estrogen level (continuous), baseline serum testosterone level (continuous), sex, and treatment order.

The following endpoints are included in the prospective analysis plan:

Table 6.1A. Endpoints for Analysis

#	Endpoint	Role	Endpoint Type	Pop	Model

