	Total Score		from 0,1,2,3,4). Higher scores represent worse outcome		
44	NPI – Apathy Doman Change Score	Exploratory biomarker predictors of response	Continuous Outcome. Higher scores represent worse apathy values.	PPP all dose groups combined	$Y_{\text{period}} = \text{Intercept} + \text{period2} + \text{subject} + \text{female} + \text{OXY}$ Linear regression model: Dependent variable: change in NPI Apathy domain scores during OXY – PLC period. Predictor variables: OXT receptor genotype, serum estrogen (baseline), serum testosterone (baseline), change in CSF_oxy, MRI regional atrophy ratings, age, sex, treatment order. -OXYTOCIN GENE rs2254298 AA vs GG vs AG -MRI atrophy ratings (frontal right, frontal left, temporal right, temporal left, etc.)
45	ACE-III	Exploratory Analysis	Continuous Outcome. Higher scores represent better cognition	PPP Most promising dose group (Q3D) from stage 1 and stage 2	$Y_{\text{period}} = \text{Intercept} + \text{period2} + \text{subject} + \text{female} + \text{OXY}$
46	ACE-III	Exploratory Analysis Supportive	Continuous Outcome. Higher scores represent better cognition	MITT Most promising dose group (Q3D) from stage 1 and stage 2	$Y_{\text{period}} = \text{Intercept} + \text{period2} + \text{subject} + \text{female} + \text{OXY}$
47	ACE-III	Exploratory Analysis	Continuous Outcome. Higher scores represent better cognition	PPP – all dose groups combined	$Y_{\text{period}} = \text{Intercept} + \text{period2} + \text{subject} + \text{female} + \text{OXY}$
48	QTcF interval as measured by ECG	Safety Outcome	Continuous < change	mitT	ECG = $Y_{\text{period}} = \text{Intercept} + \text{period2} + \text{subject} + \text{female} + \text{OXY}$ Y_{period} is QTcF interval as measured by EVG, change from baseline in each period.

49	QTcF interval as measured by ECG	Safety Outcome sensitivity	Continuous < change	miITT removing participants outside of >25 minutes post dose	$Y_{\text{period}} = \text{Intercept} + \text{period2} + \text{subject} + \text{female} + \text{OXY}$ Y_{period} is QTcF interval as measured by ECG, change from baseline in each period.
50	serum sodium level	Safety Outcome	Continuous < change	miITT	$Y_{\text{period}} = \text{Intercept} + \text{period2} + \text{subject} + \text{female} + \text{OXY}$ Y_{period} is serum sodium level, change from baseline in each period.

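### Rows 48-53 (QTcF, sodium, heart rate, blood pressure) use an MITT that, read as written, leaves out participants who stop for good in period 1; the SAP's ITT wording and ECG timing rules also conflict.

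*SAP*

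**What the plan says.** **Populations.** SAP 4.3 defines the ITT as "All participants who were randomized and completed at least one baseline assessment" and the MITT as "all participants in the ITT Population, but excluding those that did not complete at least one treatment period". In Table 6.1A the population cells of rows 48-53 are printed mitT or miITT, which can only mean the MITT. They name no dose group. Rows 55-58 (adverse events, serious adverse events, withdrawal, compliance) use the ITT, all dose groups.

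**Data after stopping.** For participants who "withdraw from the study for reasons other than death or participant or study partner consent withdrawn", SAP 5.2 asks for a visit soon after the last dose, with "identified end of treatment safety evaluations performed". It adds: "If a participant is unable to complete the EOT visit, acquired data will be included in the analysis".

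**Model.** SAP 6.2 states: "Subject is modeled as a random effect, the others are all fixed effects". The outcome is defined period by period; for row 50 it "is serum sodium level, change from baseline in each period".

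**ITT again.** SAP 6.2 also says that "the ITT analysis excludes those that did not take any study medications in their second treatment period".

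**ECG timing.** SAP 4.2 gives a per-protocol ECG analysis restricted to 0-25 minutes after dosing, and a sensitivity analysis that adds ECGs outside 15-25 minutes. Row 48 has no time window. Row 49 is a sensitivity analysis that removes participants by reference to 25 minutes after dosing.

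**The concern.** Completing a treatment period is an event after treatment starts, and harm can prevent it. Making it a condition of entry to a safety analysis selects on a possible consequence of the drug. The rule is also lopsided: the same early stop removes a participant if it happens for good in period 1 and does not if it happens in period 2. The crossover does not force this, because with a random subject effect one period's change can enter the model. The outcomes matter, since 6.1 justifies them by reported changes in QTcF, heart rate, blood pressure and sodium with intravenous oxytocin. At stake is whether the mean-change results in rows 48-53 understate harm.

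Two further conflicts leave the analyst without one rule. The two statements of the ITT describe different sets of people, and the ECG rules can give different QTcF results from the same data.

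**Working it through.** The SAP states no dropout rate or within-subject correlation, so it has no figure to reproduce. The numbers below rest on assumptions.

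**Inputs.** From SAP Section 4: 20 per arm in three arms, then 40 more. That gives n = 20 + 40 = 60 at the target schedule, or 3 x 20 + 40 = 100 over all schedules. Assumed: equal sequences; stopping rate o = 5-15% in an oxytocin period and p = 5-10% in a placebo period, in the pairs (5%, 5%), (10%, 5%), (15%, 5%) and (15%, 10%); every period-1 stopper leaves for good and has an early-termination value; within-subject correlation r from 0 to 0.8.

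**Number left out.** (n/2)(o + p):
- n = 60: 30 x 0.10 = 3.0 to 30 x 0.25 = 7.5
- n = 100: 50 x 0.10 = 5.0 to 50 x 0.25 = 12.5

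Oxytocin stoppers number (n/2)o in period 1 and (n/2)(1 - p)o in period 2, so the share left out is 1/(2 - p): 1/1.95 = 51% to 1/1.90 = 53%.

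**Effect on the estimate, r = 0.** Let stoppers on oxytocin change by s, others on oxytocin by c, and everyone on placebo by 0. With all treated, the oxytocin-placebo contrast is c(1 - o) + so in both periods. In the MITT it is c in period 1 and c(1 - o) + so in period 2, with equal weight.
- Only stoppers affected (c = 0): all treated so, MITT so/2; loss 50%.
- Stoppers affected twice as much (s = 2c): (1 + o)c against (1 + o/2)c; loss (o/2)/(1 + o) = 0.025/1.05 = 2.4% to 0.075/1.15 = 6.5%.
- All affected equally (s = c): loss 0%.
- Stoppers recovered by the visit (s = 0): (1 - o)c against (1 - o/2)c; the MITT estimate is larger by (o/2)/(1 - o) = 0.025/0.95 = 2.6% to 0.075/0.85 = 8.8%.

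**Other correlations.** Generalised least squares on expected cell counts (intercept, period, oxytocin, random subject; sex omitted, variances known):

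| Scenario | r = 0 | r = 0.2 | r = 0.5 | r = 0.8 |
|---|---|---|---|---|
| Only stoppers affected: loss | 50% | 45% | 34% | 17% |
| Stoppers affected twice as much: loss | 2.4-6.5% | 1.9-5.3% | 1.2-3.5% | 0.5-1.4% |
| All affected equally: loss | 0% | 0% | 0% | 0% |
| Stoppers recovered: MITT larger by | 2.6-8.8% | 2.1-7.0% | 1.3-4.4% | 0.5-1.7% |

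If half of the period-1 stoppers go on to complete period 2, the first row falls to about 23-24% at r = 0 and about 6% at r = 0.8. If no early-termination values exist, the loss is about nil.

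**The ITT statements.** Take someone who completes period 1 and leaves during washout. Under 4.3 this person is in both the ITT and the MITT. Under the 6.2 sentence the person is outside the ITT, so the MITT would no longer lie within the ITT from which 4.3 builds it.

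**The ECG rules.**

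| ECG time | 4.2 per-protocol (0-25) | Outside 15-25, so added by 4.2 sensitivity | Row 48 | Row 49 (ECGs after 25 minutes removed) |
|---|---|---|---|---|
| 10 min | in | yes | in | in |
| 20 min | in | no | in | in |
| 30 min | out | yes | in | out |

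The 10-minute ECG already belongs to the analysis to which the sensitivity analysis is said to add it. The 30-minute ECG enters only at the sensitivity step under 4.2 and leaves only at the sensitivity step in the table.

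**The case against.** **The exclusion may be smaller than it looks.** 4.3 does not define completing a period. If attending an early end-of-treatment visit counts, those with usable values stay in and the loss is about nil. 6.3 also says that the models use every observed value. The first point stands as an open reading. The second does not settle it, because a general statement about missing data does not override a population definition.

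**Harm that makes people stop is mostly captured elsewhere.** Adverse events, serious adverse events and withdrawals are on ITT. This stands, and it limits the point to the mean-change models of rows 48-53.

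**Early values may not show the harm.** Under 3.6 a scheduled end-of-treatment assessment follows a dose taken at that visit, whereas the 5.2 withdrawal visit comes after the last dose. Values may have recovered, and an early-termination ECG may not follow a dose at all. This stands, and including such values could dilute a signal.

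**A reader might infer that these analyses are biased towards no harm by up to half.** The documents do not support that. The 50% needs exactly zero effect in everyone on oxytocin who does not stop, together with r = 0; other equally possible patterns give little, nothing or the opposite sign.

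**A reader might also infer that 6.2 removes early leavers from the adverse-event analyses.** The sentence sits in efficacy text, directly after the statement that the supportive analysis uses the MITT, and may be a slip for MITT. But it would then contradict the 4.3 MITT definition, which keeps a participant who completed only period 1. Rows 55-58 are also the only rows that use ITT, so the conflict needs correcting either way.

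**On ECGs,** 4.2 says per-protocol, not main, and the table does label row 49 as the sensitivity analysis. That softens the reversal but leaves two windows in 4.2 and no per-protocol ECG row in the table. The 6.4 column heading that counts adverse events is clerical, since its four rows can only classify participants.

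**Conclusion.** The concern holds as a fault in stated rules, not as a demonstrated bias. As written, rows 48-53 condition on completing a period, leave out permanent period-1 stoppers, and set aside values that 5.2 plans to collect and include. This can hide harm in these analyses. How much, and even in which direction, depends on dropout, on who is affected, on recovery by the visit and on the meaning of completing a period, none of which the SAP fixes. Under the assumptions above the result runs from a 50% loss of the oxytocin effect, through none, to an MITT estimate 8.8% larger. The ITT contradiction and the ECG timing conflicts follow from the text alone and need no assumption. All three should be fixed.

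**What to change.** 1. Define a safety set: all participants who took at least one dose, analysed by treatment received in each period. Use it for rows 48-53, include available early-termination values, and state the dose group. Keep the MITT version as a sensitivity analysis, and define what completing a period means.
2. Correct the 6.2 sentence to agree with 4.3. Keep rows 55-58 on the 4.3 ITT, or move adverse events and serious adverse events to the safety set. That changes little, because the first dose is given at the baseline visit (3.6).
3. Reconcile 4.2 with rows 48-49 so that one ECG window and one main/sensitivity order apply. Both are for the sponsor to choose, before unblinding.

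The cost is SAP wording and a few population cells; no new data are needed. The downsides are slightly noisier estimates, possible dilution where values have recovered, and little gain for QTcF where an early-termination ECG does not follow a dose. Showing the MITT result alongside lets a reader see whether the choice matters.
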